4.2 Exclusion Criteria

Subjects are excluded from participation if any of the following apply:

1. Advanced periodontal disease
2. Active caries lesion(s) within 30 days prior to study drug administration (confirmed by comprehensive caries examination including standard radiographs). Subjects presenting with insipient, non-cavitated lesion(s) are not excluded.
Note: If radiographs are deemed appropriate for the study and taken within 6 months prior to the Screening visit, these may be used for determining eligibility and not required to be repeated at Screening
3. Partially erupted teeth where the entire crown is not erupted or an operculum is present
4. Medical condition (e.g., artificial heart valve, history of infective endocarditis, cardiac transplant with valvular dysfunction, congenital heart disease or total joint replacement) for which antibiotics are recommended prior to dental visits and/or procedures
5. Pathologic lesions of the oral cavity (suspicious or confirmed)
6. Full dentures or permanent orthodontic appliances, e.g., braces, buccal or lingual brackets.
Note: Partial dentures, removable retainers and night guards are not excluded, provided that they are cleaned regularly throughout the duration of the study
7. Use of systemic antibiotics, topical oral antibiotics, or use of other drugs, which in the opinion of the Investigator could influence the study outcome, beginning 30 days prior to Screening until the end of study participation
8. Medical history indicating the woman is pregnant, breastfeeding/lactating or has a positive urine pregnancy test
9. Participation in a clinical trial or receipt of a non-FDA approved therapy within 30 days prior to study drug administration (depending on the specifics, participation in an observational study is not necessarily excluded)
10. Presence of any condition or concurrent illness, which in the opinion of the Investigator, would compromise normal immune function (e.g., diabetes, rheumatoid arthritis, lupus, liver disease, organ transplant, etc.), interfere with the use of study dentifrice and oral care products, or interfere with the ability to comply with study requirements, or jeopardize the safety of the subject or the validity of the study results

5. STUDY TREATMENTS

Study subjects will receive a multiple doses of study drug (27.2 mg and [13.6 mg and/or 54.4 mg] C16G2 Varnish or Placebo). The study drug volume applied will be 1 mL or less. Study drug will be administered by qualified study staff at the center. C16G2 Varnish or Placebo will not be actively removed, but remain on the subject's teeth until removed through normal wear and mastication after discharge.

C16G2 Subjects	Placebo Subjects	Mode of Application	Days of Study Drug Admin.	C16G2 (mg)
8	3	Varnish	3	13.6
8	3	Varnish	3	27.2
8	3	Varnish	3	54.4

5.1 Study Drug

5.1.1 C16G2 Varnish Formulation

C16G2 Varnish drug product is manufactured by C3 Jian, LLC (Marina del Rey, CA) for administration as a dental varnish product. The C16G2 Varnish product is provided in two glass vials, their content is combined prior to application. One vial contains a lyophilized powder blend of C16G2 at doses of 13.6, 27.2, and 54.4 mg and other required excipients. The other vial contains a vehicle solution.

5.1.1 Placebo Varnish Formulation

Placebo Varnish is manufactured by C3 Jian, LLC (Marina del Rey, CA) and does not contain active ingredients. To maintain the study blind, the Placebo product is also provided in two glass vials, their content is combined prior to application. One vial contains a dry blend of two of the same excipients as the active vial but without C16G2. The other vial contains a vehicle solution.

For details on the C16G2 and Placebo Varnish composition refer to the Investigators Brochure.

5.1.2 Supply, Packaging, and Labeling

Study drug will be provided to the study centers in kits containing 1 dose of 13.6, 27.2 and 54.4 mg C16G2 Varnish or Placebo, 1 vial containing vehicle for reconstitution, and 4 brush applicators that should be sufficient for study drug mixing and application. Each subject will be assigned 3 kits. The packaging and labeling of the C16G2 Varnish and Placebo are identical to maintain the blind.

The boxes will contain the following material:

C16G2 Varnish or Placebo Lyophilized Powder
1 vial containing 27.2 mg, 13.6 mg or 54.4 mg C16G2 Varnish or Placebo lyophilized powder
1 vial containing 1.5 mL of V301 or V302 Varnish Vehicle
4 Brush Applicators

The varnish vial labels will include the protocol number, caution statement "Investigational New Drug Limited by (US) Law to Investigational Use Only", the kit number and the subject number/initials.

Sample C16G2 or Placebo Lyophilized Powder Vial Label

Protocol C3J16-V204-00
13.6 mg C16G2 or Placebo
Kit #: XXX Subject #/Initials _____
Caution: New Drug Limited by (US) Law to
Investigational Use Only.

Protocol C3J16-V204-00
27.2 mg C16G2 or Placebo
Kit #: XXX Subject #/Initials _____
Caution: New Drug Limited by (US) Law to
Investigational Use Only.

Protocol C3J16-V204-00
54.4 mg C16G2 or Placebo
Kit #: XXX Subject #/Initials _____
Caution: New Drug Limited by (US) Law to
Investigational Use Only.

Sample Vehicle Vial Label

Protocol C3J16-V204-00
1.5ML Varnish Vehicle
Kit #: XXX Subject #/Initials _____
Caution: New Drug Limited by (US) Law to
Investigational Use Only.

Sample Kit Box Label

The box label will include the protocol number, kit number, contents, subject number/initials, date of study drug administration, route of administration, storage temperature, caution statement "New Drug Limited by (US) Law to Investigational Use Only", and statement "Manufactured by C3 Jian, LLC., Marina del Rey, CA 90292"

Protocol C3J16-V204-00
Contents: XXX mg C16G2 Varnish or Placebo
Kit #: XXX
Subject # / Initials: _____
Date Dispensed: _____
For dental administration--Do not swallow
Store at 2-8°C
Caution: New Drug Limited by (US) Law to
Investigational Use Only
Manufactured by C3 Jian, LLC, Marina del Rey, CA,
90292

Note: Kit box label sample above is for 13.6, 27.2 and 54.4 mg C16G2 or Placebo vials

For additional details on supply, packaging and labeling refer to the Study Manual for this study.

5.2 Storage of Study Drug

All study drug material will be stored at the study site under secured conditions with limited access. Study drug boxes containing C16G2 Varnish or Placebo will be stored at 2-8°C.

Used varnish vials will be replaced in the study drug box and re-stored. Used study drug can be kept at room temperature. After dosing in the study is complete, box(es) will be sealed closed with tamper evident tape for future drug accountability by the authorized study staff and/or clinical study monitor (See Section 9.1.7).

5.3 Study Drug Preparation

Study drug is provided in a two component system consisting of study drug and vehicle, packaged in a kit. Reconstitution of study drug will be performed immediately prior to application.

5.3.1 C16G2 or Placebo Varnish Preparation

For details on study drug preparation refer to the Study Manual for this study.

Study drug preparation will be performed outside of the purview of the study subject and involves the following steps:

- Retrieve a study drug kit containing the assigned C16G2 Varnish or Placebo dose
- Enter the subject identification and dispensation date on the appropriate study drug label and study records
- Remove 1 lyophilized powder vial, 1 vehicle solution vial and 2 brushes from the study drug kit
- Manually remove the screw cap from the varnish vehicle vial
- Using a positive displacement pipet remove 1 mL of varnish vehicle from the varnish vehicle vial
- Manually remove the screw cap from the C16G2 Varnish or Placebo lyophilized powder
- Add the 1 mL of Varnish vehicle solution to the Varnish lyophilized powder vial
- Using the back end of one brush applicator quickly stir the varnish vehicle into the C16G2 or Placebo Varnish lyophilized powder until the powder is fully resuspended and there is no dry powder observed in the vial
- Dispose of the brush applicator
- A second brush applicator will be used for immediate application of C16G2 Varnish or Placebo product
- The remaining 2 brushes will be used for replacements as needed

6. STUDY ASSESSMENTS & PROCEDURES

For details on study schedules and assessments, including dosing and microbiology information refer to Appendices B through D.

6.1 Screening and Re-screening

Subjects will be screened, including *S. mutans* assessment, within 30 days of planned dosing with the study drug. If a subject qualifies for the study based on screening results, but cannot be treated within 30 days due to scheduling problems, he/she may be re-screened at the Investigator's discretion. During re-screening, the following assessments will be repeated: re-signing of the consent form (if required by the IRB), oral cavity assessment, targeted physical exam, salivary flow assessment, local laboratory (hematology and chemistry) and pregnancy test (if applicable). If the informed consent is not re-signed, all screening procedures except for the informed consent need to be within 30 days. During re-screening, the *S. mutans* assessment does not need to be repeated if <60 days have elapsed since the initial procedures. For potential subjects that do not qualify for the study based on initial screening, re-screening is at the discretion of the Sponsor in consultation with the Investigator on a case-by-case basis. If re-screened within 30 days, not all screening procedures may need to be repeated.

6.2 Subject Instructions

Enrolled subjects will be instructed to abstain from eating food and drinking beverages that contain a high sugar content (e.g., candy, soda with refined sugar, sugary snacks, dried fruit, fruit rolls) on days of study drug administration (Visits 3-5). While smokers are not excluded from study participation, subjects should abstain from using chewing tobacco throughout the study.

6.2.1 Oral Hygiene Instructions

During the entire study subjects will not be allowed to use any dental products besides the products provided by the study center. Prior to attending the study center for any visit (Visits 1-10), subjects will not be allowed to perform oral hygiene in the morning at home. In addition, Subjects will be advised not to use any mouth rinse for approximately 24 hours before the Screening visit.

Prior to discharge at Visit 2/Day -7 to -2 subjects will receive a manual toothbrush, a regular toothpaste containing fluoride, and dental floss provided by the Sponsor to take home. Subjects will be instructed to use these dental products in the morning and evening at home during the remaining study duration, including the evenings of study drug administration (Visits 3-5). In addition, subjects will be resupplied with these dental products as needed.

6.2.2 Diet Instructions

Subjects will be instructed as follows:

All Visits:

- Do not eat for 1 hour prior to the appointment time
- No liquids, other than plain water, 1 hour prior to the appointment time

Note: Subjects will be allowed to drink plain water up to 10 minutes prior to dental plaque and saliva collection, and will be instructed not to swish or rinse

Visit 3-5

Prior to Study Drug Administration

- Subjects will be instructed to not eat, drink (anything except plain water) or swish for 1 hour after the start of study drug administration
- Subjects will also be instructed to relax their jaws and refrain from grinding their teeth

Study Drug Administration

- Study drug will be prepared according to instructions provided in Section 5.3 and the Study Manual
- Study drug will be administered according to instructions provided in Appendix G and the Study Manual

Post-Study Drug Administration

- Subjects will be under the supervision of study staff to ensure that they do not consume any food or drink anything besides plain water for 1 hour after C16G2 Varnish or Placebo application. Subjects must use plastic or paper cups for water consumption, no bottles, straws or metal containers will be allowed.

6.3 Clinic Visit Schedules, Assessments & Procedures**6.3.1 Clinic Visit Schedules**

For details on Clinic Visit Schedules refer to Appendix D.

6.3.2 Assessments & Procedures**6.3.6.1 Clinic Visit 1 (Screening, Days -30 to -1)**

Subjects will be scheduled for this visit between 6AM and 10AM.

- Informed Consent/Accent & Assign Subject ID
- Inclusion/Exclusion
- Medical/Surgical/Dental History and Concurrent Illnesses
- Salivary Flow Assessment
- Concomitant Medications
- Demographics
- Dental status and comprehensive caries examination including standard radiograph
Note: If radiographs are deemed appropriate for the study and taken within 6 months prior to the Screening visit, these may be used for determining eligibility and not required to be repeated at Screening
- Screening Laboratory Testing
- Urine Pregnancy Test (females of childbearing potential only)
- Oral Cavity Assessment
- Targeted Physical Exam (general, extraoral, head & neck)
- Vital Signs (blood pressure, heart rate, temperature) taken in supine or sitting position
- Microbiology (stimulated saliva ONLY)
Note: Screening Microbiology sample will be collected on Days -30 to -8 prior to Visit 2
- Discharge

6.3.6.2 Clinic Visit 2 (Prophylaxis, Day -7 to -2)

Subjects will be scheduled for this visit between 6AM and 10AM.

- Microbiology (Stimulated Saliva and Dental plaque collection)
Note: Samples need to be obtained prior to oral hygiene training and professional dental prophylaxis
- Professional Dental Prophylaxis (prophylaxis will include removal of bulk plaque and supragingival scaling)
Note: NO fluoride treatment as part of the procedure, NO subgingival scaling as part of the prophylaxis
- Oral Hygiene Training:
 - Flossing (string): instructions are provided in Appendix E
 - Manual toothbrush technique for routine dental hygiene using a manual toothbrush provided by the sponsor and toothpaste containing fluoride (for instructions refer to Appendix F)
- Oral Hygiene Product Distribution
- Discharge

6.3.6.3 Clinic Visit 3 (Baseline, Day 0)

Subjects will be scheduled for this visit between 6AM and 10AM. Subjects should not be exposed to study drug if they present with any disruption or loss of integrity in the oral cavity mucosa, gingiva or have lip lesions, (e.g. aphthous stomatitis, active herpetic sores, cheek bites, severely chapped or cracked lips, etc.).

Pre-Dose

- Confirmation of eligibility
- Medical/Dental and Surgical History & Concurrent Illness Update
- Concomitant Medications Update
- Urine Pregnancy Test (females of childbearing potential only)
- Oral Cavity Assessment
- Targeted Physical Exam (general, extraoral, head & neck)
- Vital Signs (blood pressure, heart rate, temperature) taken in supine or sitting position
- Microbiology (stimulated saliva and dental plaque collection)
Note: Samples need to be obtained prior to oral hygiene
- Randomization
- Oral Hygiene (including brushing and flossing will be conducted at the clinic prior to study drug administration)

Study Drug Administration:

Instructions for the preparation of C16G2 Varnish or Placebo are provided in the Study Manual. Instructions for the application of study drug are provided in Appendix G.

- At Visit 3/Day 0, subjects will receive a single study drug administration. Subjects will have C16G2 Varnish or Placebo applied to all tooth surfaces.
Note: C16G2 Varnish or Placebo will not be actively removed, but remain on the subject's teeth until removed through normal wear and mastication after discharge

Post-Dose

- Photographic imaging immediately after study drug application (see instructions in Appendix H)
- Oral Cavity Assessment (hard and soft tissues)
- Vital Signs (blood pressure, heart rate, temperature) taken in supine or sitting position 1 hour (\pm 15 minutes) post study drug administration
- Subjects will not eat, swish, or drink anything besides plain water from study drug administration to one hour after study drug application. In addition, subjects will be advised to relax their jaws and to not grind their teeth. Subjects will be supervised to ensure compliance
- Adverse Events
- Discharge

6.3.6.4 Clinic Visit 4 (24-48 hrs Post Visit 3) & Visit 5 (24-48 hrs Post Visit 4)

Subjects will be scheduled for these visits between 6AM and 10AM. Subjects should not be exposed to study drug if they present with any disruption or loss of integrity in the oral cavity mucosa, gingiva or have lip lesions, (e.g. aphthous stomatitis, active herpetic sores, cheek bites, or severely chapped or cracked lips, etc.).

Pre-Dose

- Concomitant Medications Update
- Vital Signs (blood pressure, heart rate, temperature) taken in supine or sitting position
- Microbiology (stimulated saliva and dental plaque collection)
- Oral Cavity Assessment (hard and soft tissues)
- Targeted Physical Exam (general, extraoral, head & neck) (Visit 4 ONLY)
- Oral Hygiene (including brushing and flossing will be conducted at the clinic prior to study drug administration)

Study Drug Administration:

Instructions for the preparation of C16G2 Varnish or Placebo are provided in the Study Manual. Instructions for the application of study drug are provided in Appendix G.

- Subjects will receive a single study drug application. Subjects will have C16G2 Varnish or Placebo applied to all tooth surfaces.

Note: C16G2 Varnish or Placebo will not be actively removed, but remain on the subject's teeth until removed through normal wear and mastication after discharge

Post-Dose

- Photographic imaging immediately after study drug application (see instructions in Appendix H).
- Oral Cavity Assessment (hard and soft tissues)
- Vital Signs (blood pressure, heart rate, temperature) taken in supine or sitting position 1 hour (\pm 15 minutes) post study drug application
- Subjects will not eat, swish, or drink anything besides plain water for one hour after study drug application. In addition, subjects will be advised to relax their jaws and to not grind their teeth. Subjects will be supervised to ensure compliance.
- Adverse Events
- Discharge

6.3.6.5 Clinic Visits 6-8 (24 hours, 3 days and 7 days Post Visit 5)

Subjects will be scheduled for this visit between 6AM and 10AM

- Concomitant Medication Update
- Oral Cavity Assessment (Visit 6 and 8 ONLY)
- Targeted Physical Exam (Visit 6 and 8 ONLY)
- Microbiology (stimulated saliva and dental plaque collection)
- Adverse Events
- Discharge

6.3.6.6 Clinic Visits 9 & 10 (Week 2 & 4 Post Visit 5)

Subjects will be scheduled for this visit between 6AM and 10AM.

- Microbiology (stimulated saliva and dental plaque collection)
- End of Study (Visit 10 only)

Study Visit Schedule

STUDY PERIODS	VISIT #	SCHEDULE	TIME
Screening	1	Day -30 to -1	Morning (6-10 AM)
Prophylaxis	2	Day -7 to -2	Morning (6-10 AM)
Study Drug Administration	3 4 5	Day 0 24-48 hrs Post Visit 3 24-48 hrs Post Visit 4	Morning (6-10 AM)
Safety and Microbiology Follow-up	6 7 8	24 hours Post Visit 5 3 days Post Visit 5 7 Days ± 1 Day Post Visit 5	Morning (6-10 AM)
Microbiology Follow-up	9 10	14 Days ± 2 days Post Visit 5 28 Days ± 3 days Post Visit 5	Morning (6-10 AM)

7.2 Assessment of Severity (Intensity) of Adverse Events

The severity or intensity of an AE describes the degree of impact upon the subject and/or the need for, and the extent of medical care required to treat the AE.

Symptoms should be graded as mild, moderate, severe, or life threatening according to the grading scale noted in Table 1. Please refer to Common Terminology Criteria for Adverse Events (CTCAE) Version 4.0.

Table 1: Adverse Events Intensity Description

Grade	Description
Mild (1)	Generally non-progressive; transient or mild discomfort; no limitation in activity; no medical intervention/therapy required.
Moderate (2)	Mild to moderate limitation in daily activity; some assistance may be needed; no or minimal medical intervention/therapy required.
Severe (3)	Marked limitation in daily activities; some assistance usually required; medical intervention/therapy required.
Life Threatening (4)	Extreme limitation in daily activities; significant assistance required; significant medical intervention required.

Note the distinction between the severity and the seriousness of an AE. A severe event is not necessarily a serious event. For example, a headache may be severe (interferes significantly with

subject's usual function), but would not be classified as serious unless it met the criteria for an SAE (See Section 7.7).

7.3 Assessment of Causality (Relationship to Study Drug)

An Investigator's causality assessment is the determination of whether there exists a reasonable possibility that the study drug caused or contributed to an AE. The Investigator's assessment of causality must be provided for all AEs (serious and non-serious).

Several factors to consider when assessing the relationship of an event to the study drug:

- Alternative etiology - Is the event due to the underlying disorder being studied or to another known disorder?
- Known relationship - Has the event been observed before in patients treated with this study drug or similar products?
- Temporal relationship - Is there a reasonable temporal relationship between the time of onset of the event and the administration of the study drug?
- Concomitant medication - Is the event a known side effect of a concomitant medication?

The Investigator will document his/her opinion of AE relationship to study drug using the criteria outlined in Table 2 below.

Table 2: Adverse Event Relationships Description

Relationship	Description
None	The event can be readily explained by the subject's underlying medical condition, a concomitant therapy or other cause and the Investigator believes no relationship exists between the event and study drug. In this case, the Investigator should document the condition, concurrent / underlying illness, medication, study procedure or other cause they believe to be the cause of the adverse event.
Unlikely	The event does not follow a reasonable temporal sequence from administration of study drug nor does the event follow a known or expected response pattern to study drug and may have another cause. In this case, the Investigator should document the condition, concurrent / underlying illness, medication, study procedure or cause they believe may have contributed to the adverse event.
Possible	The subject's condition, concurrent/underlying illness, medication, or study procedures cannot explain the event, and there is a plausible temporal relationship between the event and study drug administration.
Probable	The temporal relationship between the administration of study drug and the adverse event strongly suggests a relationship, and/or the adverse event cannot be reasonably explained by another condition, concurrent / underlying illness, medication, study procedure or other cause, or the adverse event abates with discontinuation of study drug, and recurs with re-administration.

For reporting purposes, AEs assigned a relationship to study drug of "Probable," and "Possible" will be classified as related to study drug. AEs assigned a relationship to study drug of "Unlikely" and "None" will be classified as not related to study drug.

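### Table 2 defines *Possible* more narrowly than Section 7.3's own causality standard, so an event with plausible timing and a sufficient competing cause meets no grade

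*Combined protocol and SAP*

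**What the plan says.** Section 7.3 of the protocol defines the causality assessment as a judgement of "whether there exists a reasonable possibility that the study drug caused or contributed to an AE". It makes that judgement compulsory: the Investigator's "assessment of causality must be provided for all AEs (serious and non-serious"). The opinion is to be recorded using the criteria in Table 2, and no default is given for an event that fits no row.

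The four rows of Table 2 read, in substance:

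- *None*: the event is readily explained by another cause, and "the Investigator believes no relationship exists between the event and study drug".
- *Unlikely*: there is no reasonable temporal sequence, "nor does the event follow a known or expected response pattern to study drug and may have another cause".
- *Possible*: the subject's condition, illness, medication or "study procedures cannot explain the event, and there is a plausible temporal relationship between the event and study drug administration".
- *Probable*: the timing "strongly suggests a relationship, and/or the adverse event cannot be reasonably explained by another condition" or other listed cause, or "the adverse event abates with discontinuation of study drug, and recurs with re-administration".

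Section 7.3 then counts *Probable* and *Possible* as related, while an event graded *Unlikely* or *None* "will be classified as not related to study drug". Section 7.4 uses the same split to decide which events are suspected adverse reactions (SARs). Section 8.7.6.1 plans a tabulation of adverse events by related and unrelated, and Section 7.8 applies the same criteria to SAE updates.

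**The concern.** The standard and the table use different tests. Under the standard, a drug that contributed alongside something else can still be a reasonable possibility. Under the *Possible* row, an alternative that could explain the event closes that row, however plausible the timing. An event of this kind has to be given a grade whose wording it does not satisfy, and that choice decides whether it enters the related column and whether it is a SAR.

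Safety is the primary objective (Section 2), and Section 8.3 leaves the Investigator unblinded, so the choice is made with the treatment known.

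The design makes such events realistic. Every subject has a prophylaxis with supragingival scaling 2-7 days before the first application (Sections 3 and 6.3.6.2), then brushes and flosses morning and evening (Section 6.2.1). Take gum or tooth discomfort first reported at Visit 4, 5 or 6, 24 hours or more after an application. It has plausible timing and a study procedure that could account for it. Section 1.1.2 reports that gingival swelling, oral discomfort and tooth sensitivity were judged related in an earlier gel study, in which 3 active and 2 placebo subjects had related events.

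**Working it through.** The plan gives no figure to reproduce, so the check is one of logic.

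**Test event.** (a) Timing is plausible but does not strongly suggest the drug. (b) The subject's condition, medication or a study procedure could by itself explain the event. (c) There is no abatement and recurrence on re-administration. (d) The Investigator does not rule the drug out.

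| Grade | Condition that decides | Result |
|---|---|---|
| *None* | Investigator believes there is no relationship | fails on (d) |
| *Unlikely* | no reasonable temporal sequence | fails on (a) |
| *Possible* | other causes cannot explain the event | fails on (b) |
| *Probable* | strong timing, and/or no reasonable alternative, or recurrence | fails on (a), (b) and (c) |

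No row is met. The result is the same whether or not the event follows a known response pattern.

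**Where the gap ends.** If the Investigator judges that the alternative only contributed and could not alone explain the event, *Possible* is met. With *and/or* in the *Probable* row read as *or*, strongly suggestive timing also closes the gap. Read as *and*, strong timing with a competing cause and no recurrence fails as well, so the gap is wider.

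**Completeness check.** Crossing timing (3 levels) with four yes/no items (alternative cause, known pattern, recurrence, Investigator believes no relationship) gives 3 × 2 × 2 × 2 × 2 = 48 combinations. Under the *or* reading, 3 meet no row, and 2 of these are the test event with and without a known pattern. The third has no reasonable timing but a known pattern. These counts only confirm that the gap exists.

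**Check of the rewording.** Let *Possible* require at least plausible timing and a drug not ruled out, whether or not an alternative exists. The combinations that newly meet it have an alternative cause, a drug not ruled out and plausible or strong timing: 2 (timing) × 2 (pattern) × 2 (recurrence) = 8. Under *or*, 6 of the 8 already meet *Probable*: 4 with strong timing and 2 with plausible timing and recurrence. The other 8 − 6 = 2 are the gap. None of the 8 meets *None* (the drug is not ruled out) or *Unlikely* (the timing is reasonable), so no new related/not-related conflict arises.

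**Secondary observation.** With *and/or* read as *or*, and the alternative causes treated as one item, every event that meets *Possible* also meets the no-reasonable-alternative limb of *Probable*. Both grades count as related, so the related count does not change.

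**Scale of one subject.** Each cohort has 8 active and 3 placebo subjects (Section 5). One subject is 1/8 = 12.5 percentage points of the active arm or 1/3 = 33.3 points of its placebo group. That is true of any single reclassification.

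**The case against.** The best reply is that Table 2 records an opinion, formed after weighing four listed factors that include known relationship and alternative etiology. A sensible Investigator would read the *Possible* row as meaning that other causes cannot fully explain the event, and would use it. That narrows the gap in practice. But it is not what the row says, and in a multi-centre study two Investigators could grade the same event differently and both cite the table.

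The second reply is that little depends on it, and this largely stands. The analysis is descriptive (Section 8.1), and cohort progression rests on microbiology (Sections 3.1.1 and 8.2). SAEs go to the sponsor within 24 hours whatever the relationship (Section 7.8). The single-dose varnish study reported only two adverse events (Section 1.6).

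A reader might infer three stronger things that the documents do not support:

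- **That unblinded grading will push events toward not related.** Nothing in the documents shows the direction of any bias.
- **That the larger fault is an overlap between *None* and *Probable*.** The wording does allow an event to meet both. But the same Investigator would have to believe there is no relationship while judging the timing strongly suggestive, or while accepting a recurrence after discontinuation. Three single applications 24-48 hours apart, with varnish left to wear off, hardly allow such a rechallenge.
- **That the share of combinations with no grade measures how often this will happen.** It does not, because the combinations are not equally likely.

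**Conclusion.** The point holds as a conflict between Section 7.3's standard and its lowest related grade. It leaves one realistic type of event without a grade, and that event's related and SAR status then depends on an unwritten choice. It should be corrected, because it feeds a planned tabulation under the primary objective and the correction is easy.

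Its size in events cannot be estimated from the documents and may be small. All-cause TEAE incidence and the by-subject listings do not depend on the grade, so the safety evaluation as a whole is not undermined.

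The conclusion rests on reading the *Possible* row literally, on timing that is plausible but not strongly suggestive (under the *or* reading of *Probable*), and on an alternative that could explain the event by itself.

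**What to change.** Reword *Possible* along these lines: the temporal relationship to study drug is at least plausible and the drug cannot be ruled out as a cause or contributor (*None* is not met), whether or not the subject's condition, medication or study procedures could also explain the event. Ask the Investigator to document the competing cause under *Possible*, as Table 2 already does under *None* and *Unlikely*. Keep *Possible* and *Probable* together as related. The sponsor may also tidy the *and/or* in *Probable* so that the two grades are distinct.

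I would not add a rule that recurrence excludes *None* or *Unlikely*. Photographs follow every application and carry a listed risk of lip soreness (Section 1.6), so recurrence may reflect the procedure.

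The cost is a few lines in Table 2 and brief site training. Related-AE and SAR counts may look slightly less favourable: with dosing over about 5 days (synopsis) and 1 week of safety follow-up, many TEAEs can have plausible timing. The documented competing causes would let a reader see why.
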